9.1.4 Exploratory Subgroup Analyses (Primary Endpoint)

Subgroup analyses by age group (≤ 65 , > 65 years), sex, race (white, other), region (Europe, NA), history of hospitalization for acute decompensation of liver cirrhosis (yes, no), CLIF-C AD group (CLIF-C AD score > 50 , CLIF-C AD score ≤ 50), time to randomization from start of screening (≤ 3 days, > 3 days), ethnicity (Hispanic, non-Hispanic), country and European region (East Europe, West Europe, [see appendix 3](#) for details) will be carried out for the primary endpoint based on the ITT population.

In each defined subgroup category, the analysis will be carried out using the same methodology as outlined in [Section 9.1.2](#), and the hazard ratio and CI for the subgroup will be estimated. When the subgroup is defined by a stratification factor used for the randomization, the stratification factor will not be used in the stratified Cox PH model. For example, in the analysis of region or country subgroup, only the history of hospitalization for acute decompensation of liver cirrhosis (yes or no) will be used as the stratification factor in the stratified Cox PH model.

These results will be considered exploratory, due to both multiplicity concerns and small sample sizes that cannot be pre-specified. Only summary statistics and CIs will be presented; p-values will not be determined. A minimum of 30 subjects must be present in each subgroup category for the analysis to be performed.

The subgroup analysis based on the ITT population will be repeated for the per-protocol population.

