6.2 Sample Size

Based on the CANONIC study, the overall 1-year transplant-free mortality rate in the current study population is assumed to be about 46% (11,16). Assuming a potential drop-out rate of 20% and 5% type-1 error for a 2-sided Chi-square test, a global sample size of 410 patients (205 per treatment group) will allow an 80% statistical power to detect an absolute reduction of 15% (17) for the 1-year mortality rate in subjects treated with SMT + Albutein 20%.

GRIFOLS	Number	IG1601	Version	2.0	Status	Effective	Effective Date	09-Sep-2024	Page	22 of 52
BIG-CL-SP-000319 IG1601 Statistical Analysis Plan										

GRIFOLS	Number	BIG-CL-SP-000319		Version	2.0	Status	Effective	Effective Date	09-Sep-2024	Page	23 of 52
	IG1601 Statistical Analysis Plan										

Alternatively, the sample size was calculated based on the log-rank test as follows. Assuming the 1-year transplant or mortality rate is 46% for the control group, or equivalently, the transplant-free survival rate is 54%, which translates to a hazard rate of 0.0017 assuming an exponential distribution. Using a log-rank test at the 2-sided significant level of 5%, a total of 125 events would provide at least 80% power to detect an absolute reduction of 15% in transplant or mortality rate (a 31% 1-year transplant or mortality rate, or equivalently, a 69% transplant-free survival rate) in subjects treated with SMT + Albutein 20%. This absolute difference in transplant or mortality rates translates to a hazard ratio of 0.6022, or an approximate 40% risk reduction. With all subjects followed for the entire 1-year duration of the study, a total of 322 subjects would be required to obtain 125 events. Assuming a dropout rate of 20%, a global sample size of 404 subjects (202 per treatment group) is required. This sample size calculation was performed using Proc Power with the two-sample survival statement in SAS version 9.4.

Taking a conservative approach, the larger of the 2 sample sizes (i.e., 410 subjects based on the Chi-square test) will be used to ensure the study has sufficient power.

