9.2.8 Exploratory Subgroup Analyses (Secondary Endpoints)

Exploratory subgroup analyses for the subgroup categories outlined in [Section 9.1.4](#) will be performed for the time to death through 1 year after randomization secondary efficacy outcome described in [Section 9.2.1](#). The subgroup analyses will be performed for both the ITT population and the per-protocol population. Because hypothesis testing is not performed and p-values are not reported for subgroup analyses, the fixed-sequence testing methodology does not apply to subgroup analyses.

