Since this study is a large multinational study with varying rates of recruitment between countries, a subgroup analysis will be conducted for countries with reasonably large number of patients (30 patients). The objective of these analyses is to examine whether the patients in different countries benefit differently from the treatment possibly due to different standard medical treatment. This subgroup analysis is incorporated in the appropriate sections above (See [Section 9.1.4](#)). We do not conduct this subgroup analysis for countries with fewer patients because the model may not converge due to the fact that uncertainties in the parameter estimates become larger due to small sample size. For European countries an additional grouping based on the region in Europe the countries are located will be applied and subgroup analyses will be performed.

Rationale and plan for subgroup analysis based on time from start of screening to randomization with first treatment with IP

The time window from screening to first administration of Albutein 20% in the treatment arm has varied with protocol amendments. The final protocol amendment under which most of the patients were enrolled dictates that patients are randomized and receive first dose of IP within 3 days (72 hours) of start of screening, whereas earlier versions allow for the first dose of IP to occur more than 3 days (72 hours) after start of screening. To account for any possible differential treatment effect based on time to treatment with IP, a subgroup analysis will be done comparing subjects with time to randomization from start of screening ≤ 3 days vs time to randomization from start of screening >3 days. This subgroup analysis is incorporated in the appropriate sections above (See [Section 9.1.4](#)).

Discussion of the definition of TEAE in the SAP

In the protocol, a TEAE is defined as an AE which occurs between the start of study treatment and the final visit of the clinical study. In this SAP, TEAEs are defined as AE

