with onset date/time on or after the subject's randomization date/time for SMT arm, and with onset date/time during or after the first dose administration for the SMT + Albutein 20% arm. For subjects in the SMT + Albutein 20% arm, the first dose is scheduled on the same day as randomization. The definition is modified because the treatment time after randomization entered in the EDC for subjects in the SMT arm may not be on day 1, which may cause bias in the comparison of TEAE between the two groups. The new definition assumes that subjects in the SMT group had been on the SMT treatment before entering the trial. The new definition intends to remove bias in the comparison of TEAE between two treatment groups.

Changes in the analysis of longitudinal outcomes

The MMRM will be used to analyze the longitudinal continuous outcomes [e.g., CLIF-C OF score, CLIF-C ACLF score, CLIF-C AD score, MELD score, EQ-5D-5L index score, EQ-5D-5L VAS score], and general linear model implemented in SAS Proc GENMOD will be used to analyze the longitudinal binary or ordinal outcomes [Child-Pugh Score, Incidence of disease-related complications, Incidence of insertion of TIPS for refractory ascites]. However, as stated in Section 9.1.2.3 of the protocol, exploratory endpoints would be analyzed by means of ANCOVA or Student's t tests (for normally-distributed variables), non-parametric Mann-Whitney U test (for non-parametric variables), and Fisher's exact test or Chi-square test (for binomial variables). The methods specified in the protocol are not suitable for longitudinal outcomes with missing data.

Adding Ethnicity as a new subgroup analysis

The Ethnicity is collected in EDC. To account for any possible differential treatment effect based on ethnicity, a subgroup analysis will be done comparing Hispanic subjects vs non-Hispanic subjects. This subgroup analysis is incorporated in the appropriate sections above (see [Section 9.1.4](#)).

GRIFOLS	Number	BIG-CL-SP-000319	
	Version	2.0	
	Status	Effective	
	Effective Date	09-Sep-2024	
	Page	46 of 52	

13 References

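### SAP Section 12 asks whether the treatment effect differs by country, time to randomization and ethnicity, but Sections 9.1.4 and 9.2.8 plan no estimate of that difference

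*SAP*

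**What the plan says.** SAP Section 12 (Changes in Planned Analysis) gives the purpose of several subgroup analyses, each time as a comparison of treatment effects:

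- Country: to "examine whether the patients in different countries benefit differently from the treatment possibly due to different standard medical treatment". European region (East or West) is added as a further grouping.
- Time from screening to randomization (up to 3 days, or longer): "To account for any possible differential treatment effect based on time to treatment with IP".
- Ethnicity (Hispanic or not): "To account for any possible differential treatment effect based on ethnicity".
- CLIF-C AD score (above 50, or not): to see whether the intervention acts differently by score, on the primary and the secondary endpoints.

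Section 9.1.4 sets out the analysis for ten factors. The stratified Cox analysis of Section 9.1.2 is repeated inside each category that has at least 30 subjects, and that category's hazard ratio and CI are given. The results are labelled exploratory, and "Only summary statistics and CIs will be presented; p-values will not be determined". Section 9.2.8 does the same for time to death through 1 year and places it outside the fixed sequence: "Because hypothesis testing is not performed and p-values are not reported for subgroup analyses".

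One factor is treated differently. Section 9.1.3 fits a stratified Cox model with treatment, CLIF-C AD category and their interaction, for the primary endpoint, in the ITT and per-protocol populations. Section 9.2.8 plans no interaction for any factor.

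**The concern.** Whether two categories benefit differently is a question about the ratio of their hazard ratios. A separate CI in each category describes that category's own effect and says nothing directly about the ratio. For country, timing and ethnicity, and for CLIF-C AD on survival, the planned tables therefore leave out the quantity that Section 12 names.

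The risk lies in how such tables are read. A common habit is to note which intervals exclude 1, and that depends heavily on how many events each category has. Under a uniform effect, the larger category tends to show a benefit and the smaller one tends not to. In a multinational trial where standard treatment is left to each institution, such a pattern invites a claim that the effect depends on country, timing or ethnicity. The same tables cannot support a claim of consistency either.

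**Working it through.** **Inputs, SAP Section 6.2.** "Assuming the 1-year transplant or mortality rate is 46% for the control group"; "a 31% 1-year transplant or mortality rate, or equivalently, a 69% transplant-free survival rate" on Albutein; "Using a log-rank test at the 2-sided significant level of 5%, a total of 125 events would provide at least 80% power"; 20% dropout; 410 subjects randomized 1:1.

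**The plan's own figures first.**

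- HR = ln(0.69)/ln(0.54) = 0.6022, as stated. ln HR = −0.507.
- Schoenfeld events = 4(1.960 + 0.842)²/0.507², which rounds up to 123. Freedman's formula gives 128. The stated 125 lies between them, and Schoenfeld power at 125 events is 80.9%.
- The mean event rate is (0.46 + 0.31)/2 = 0.385. Then 322 × 0.385 = 124 events and 410 × 0.8 × 0.385 = 126 events.

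The design is reproduced, so 125 events is a fair base.

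**Assumption.** The documents give no subgroup shares. Let the larger category hold a share f of D events, with the same HR of 0.6022 in both categories.

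**Reading each CI against 1.** The chance that a category's 95% CI excludes 1 is about Φ(√d × 0.507/2 − 1.96), with d the events in that category. The categories share no subjects, so P(exactly one excludes 1) = p₁(1 − p₂) + p₂(1 − p₁).

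| Split of events | p₁ / p₂ (D = 125) | Exactly one excludes 1 (D = 125) | Same, D = 158 (410 × 0.385, no dropout) |
|---|---|---|---|
| 50/50 | 52% / 52% | 50% | 47% |
| 70/30 | 66% / 34% | 55% | 54% |
| 80/20 | 72% / 24% | 61% | 63% |
| 90/10 | 77% / 14% | 69% | 74% |

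- Among trials with a significant overall result, simulation from the same normal approximation (D = 125) gives 57% at 50/50 and 81% at 90/10.
- For k equal-sized countries, the chance that the CIs do not all agree is 1 − pᵏ − (1 − p)ᵏ: 70% for three countries (p = 0.373) and 77% for eight (p = 0.169).
- At the 30-subject minimum, 30 × 0.8 × 0.385 ≈ 9 events. A CI centred on 0.60 then runs from about 0.17 to 2.2.
- If the true HR is 1 everywhere, the two-category figure is only 2 × 0.05 × 0.95 = 9.5%.

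**Using the contrast instead.** The log ratio of hazard ratios has SE = √(4/(Df) + 4/(D(1 − f))). Under a uniform effect its 95% CI excludes 1 in 5% of trials, whatever the split. In the simulation, about 90% to 95% of the pairs with only one CI excluding 1 had a non-significant interaction.

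**What the contrast can detect (D = 125).** The SE is 0.358 at 50/50 and 0.447 at 80/20. Power for HR 0.6022 in one category against 1.0 in the other is Φ(0.507/SE − 1.96) = 29% and 20%. The ratio detectable with 80% power is exp(2.80 × SE) = 2.7 and 3.5.

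**The case against.** The strongest reply is that the SAP already guards against misuse. It calls these analyses exploratory because of multiplicity and small samples, gives no p-values and disclaims hypothesis testing. A reader might infer that the plan tests HR = 1 within each subgroup. It does not, and the misreading measured above would be the reader's. This part stands. But the exploratory label deals with multiplicity and leaves open which quantity is estimated, and a ratio of hazard ratios with a CI needs no p-value.

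A reader might also infer that the SAP never compares subgroups. Section 9.1.3 does so for CLIF-C AD on the primary endpoint, the factor tied to the eligibility change.

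The categories are disjoint, so anyone can derive the ratio and its CI from two published hazard ratios and CIs. That is true. The information is not lost, but the plan leaves to the reader the one comparison that Section 12 promises.

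Age, sex, race, region and hospitalization history are routine protocol subgroups with no stated aim of finding a differential effect. That stands, and the point is not pressed for them.

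Lastly, interaction power is low, and ten independent unadjusted interaction tests would carry a 1 − 0.95¹⁰ = 40% chance of at least one false positive. This is a good reason to report estimates with CIs and no tests. It does not favour leaving the estimate out, since a wide interval shows plainly how little the data can say.

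**Conclusion.** There is a real mismatch between the purpose in Section 12 and the output in Sections 9.1.4 and 9.2.8. It covers country with European region, time to randomization and ethnicity, and CLIF-C AD for time to death. Section 9.1.3 shows that the SAP already has a suitable method.

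If the separate CIs are read against 1, a uniform effect looks differential in about 50% to 69% of two-category factors, against about 5% for an interaction contrast. Those figures assume the design HR of 0.6022, about 125 events and event splits from 50/50 to 90/10, none of which the documents state for any subgroup. A reader might infer that a uniform effect will usually look differential. The documents do not support that as a general statement: at an even split it is about an even chance (47% with 158 events), and with no treatment effect it is 9.5%.

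The primary analysis, the fixed sequence, the sample size and the data collected are not affected. The change is worth making because it is cheap and answers the SAP's own question.

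**What to change.** - **Section 9.1.4:** extend the Section 9.1.3 interaction model to at least European region (European subjects only), time to randomization and ethnicity. Report the ratio of hazard ratios with its 95% CI. For country, report a simple heterogeneity estimate across countries with at least 30 subjects. A random-effects model with shrunken country estimates is optional.
- **Section 9.2.8:** do the same for time to death through 1 year, and add CLIF-C AD there.
- **Both sections:** keep the exploratory label, give no p-values, and state that a differential effect is judged from these contrasts and not from whether single CIs include 1.
- **If the model is also used for region or hospitalization history:** keep the factor as a stratum and include only treatment and the treatment-by-factor term. The factor's main effect cannot be estimated when it is a stratum, but the interaction can.

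The cost is a SAP wording change and a few extra models on data already collected. The interaction CIs will be wide (20% to 29% power for HR 0.60 against 1.0), so the change guards against false claims of difference but will not make real differences easy to detect.

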9.2 Secondary Endpoints

The analysis of the secondary endpoints will be performed for the ITT population. A fixed-sequence testing method will be used for the analysis of secondary endpoints, as described in [Section 6.5](#). The secondary endpoint definitions are presented in the order in which testing will be performed.

GRIFOLS	Bioscience Industrial Group	Number	IG1601	Statistical Analysis Plan
		Version	2.0	Status
		Effective	09-Sep-2024	Page
		30 of 52		

A sensitivity analysis will be performed for each of the secondary endpoints using the PP population.

9.2.1 Time to Death Through 1 Year After Randomization

Time to one-year survival will be calculated as [date of death – randomization date + 1] for those subjects who died within the analysis period. Subjects who did not die within the analysis period will have their time to event censored at the earlier of the following times:

- Date of last contact.
- Cut-off date for analysis.

This endpoint will be analyzed in the same way as outlined in [Section 9.1.2](#) for the primary analysis.

9.2.2 Time to Liver Transplantation or Death Through 6 Months After Randomization

Time to 6 Months transplant-free survival will be calculated as the earlier of [(date of liver transplantation or date of death) – randomization date + 1] for those subjects who died or had a liver transplant within the analysis period. Subjects who neither died nor had a liver transplant within the analysis period will have their time to event censored at the earlier of the following times:

- Date of last contact.
- Cut-off date for analysis.

This endpoint will be analyzed in the same way as outlined in [Section 9.1.2](#) for the primary analysis. The probability of event-free survival for the endpoint at day 31, 61, 91, 181 for the endpoint and 95% confidence interval (CI) will be estimated.

9.2.3 Time to Death Through 6 Months After Randomization

Time to 6 Months survival will be calculated as [date of death – randomization date + 1] for those subjects who died within the analysis period. Subjects who did not die within the analysis period will have their time to event censored at the earlier of the following times:

- Date of last contact.
- Cut-off date for analysis.

This endpoint will be analyzed in the same way as outlined in [Section 9.1.2](#) for the primary analysis. The probability of event-free survival for the endpoint at day 31, 61, 91, 181 for the endpoint and 95% confidence interval (CI) will be estimated.

GRIFOLS	Number	IG1601	BIG-CL-SP-000319
	Version	2.0	Status
	Effective Date	09-Sep-2024	Page
		31 of 52	

Number	BIG-CL-SP-000319	Version	2.0	Status	Effective	Effective Date	09-Sep-2024
							32 of 52
GRIFOLS	Bioscience Industrial Group						
IG1601	Statistical Analysis Plan						

9.2.4 Time to Liver Transplantation or Death Through 3 Months After Randomization

Time to 3 Months transplant-free survival will be calculated as the earlier of [(date of liver transplantation or date of death) – randomization date + 1] for those subjects who died or had a liver transplant within the analysis period. Subjects who neither died nor had a liver transplant within the analysis period will have their time to event censored at the earlier of the following times:

- Date of last contact.
- Cut-off date for analysis.

This endpoint will be analyzed in the same way as outlined in [Section 9.1.2](#) for the primary analysis. The probability of event-free survival for the endpoint at day 31, 61, 91 for the endpoint and 95% confidence interval (CI) will be estimated.

9.2.5 Time to Death Through 3 Months After Randomization

Time to 3 Months survival will be calculated as [date of death – randomization date + 1] for those subjects who died within the analysis period. Subjects who did not die within the analysis period will have their time to event censored at the earlier of the following times:

- Date of last contact.
- Cut-off date for analysis.

This endpoint will be analyzed in the same way as outlined in [Section 9.1.2](#) for the primary analysis. The probability of event-free survival for the endpoint at day 31, 61, 91 for the endpoint and 95% confidence interval (CI) will be estimated.

9.2.6 Total Number of Paracenteses

For each subject, the total number of reported paracentesis procedures on treatment will be calculated and summarised by treatment group.

A paracentesis procedure occurring on treatment will be defined as any paracentesis procedure that occurred with a start date/time on or after the subject's date/time of randomization (for SMT alone group) or commencement of Albutein (for SMT+ Albutein treatment group). If time is missing and the procedure occurred on or after the date of randomization (for SMT alone group) or the date of commencement of Albutein

(for SMT+ Albutein treatment group) it will be considered to have occurred while on treatment.

The rate of occurrence of paracenteses will be analyzed using Poisson regression with adjustment for overdispersion using the Pearson statistic to estimate the scale parameter.

- Null hypothesis H_0 : The rate of occurrence of paracentesis procedures SMT + Albutein 20% is greater than or equal to the rate of occurrence of paracentesis procedures on SMT alone. [i.e. $Rate\ ratio\ (SMT+Albutein\ 20\% \ vs \ SMT\ Alone) \geq 1$].
- Alternative hypothesis H_a : The rate of occurrence of paracentesis procedures on SMT + Albutein 20% is less than the rate of occurrence of paracentesis procedures on SMT alone. [i.e. $Rate\ ratio\ (SMT+Albutein\ 20\% \ vs \ SMT\ Alone) < 1$].

The rate of occurrence of paracentesis procedures in the SMT + Albutein 20% treatment group will be compared to the rate of occurrence of paracentesis procedures in the SMT alone group. The response variable in the model will be the total number of procedures experienced by a subject while on treatment. The model will include treatment group, IWRS stratification factors of region (Europe or North America) and history of hospitalization for acute decompensation of liver cirrhosis (yes or no) as factors. The logarithm of the subjects' treatment duration will be used as an offset variable in the model to adjust for subjects having different exposure times during which the events could occur. The estimated treatment effect (i.e. the incidence rate ratio of SMT + Albutein 20% versus SMT alone) and corresponding 95% confidence interval (CI) will be presented.

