6.5 Hypothesis Testing and Multiplicity Adjustments

All statistical tests will be 2-sided with significance level fixed at 0.05.

The fixed-sequence testing method will be used to adjust for multiplicity in the analyses of the secondary efficacy endpoints (using the ITT population). Specifically, the superiority of SMT + Albutein 20% versus SMT alone for the secondary efficacy endpoints will only be tested if the superiority for the primary efficacy endpoint is demonstrated at the 2-sided significance level of 5% (for ITT population).

For the secondary efficacy endpoints, each subsequent hypothesis is tested only if the superiority for the previous comparison(s) listed below has been demonstrated at a 2-sided significance level of 5%. The order in which the null hypotheses will be tested is predetermined for the secondary efficacy endpoints as follows:

1. Time to death through 1 year after randomization
2. Time to liver transplantation or death through 6 months after randomization
3. Time to death through 6 months after randomization
4. Time to liver transplantation or death through 3 months after randomization
5. Time to death through 3 months after randomization
6. Total number of paracenteses
7. Incidence of refractory ascites according to the ICA criteria

No other adjustments for multiplicity are planned. P-values will be displayed for all the above pre-specified tests for completeness; interpretation and reporting of significant hypothesis test results will follow the fixed sequence approach described.

GRIFOLS	Bioscience Industrial Group	Number	IG1601	Version	2.0	Status	Effective	Effective Date	09-Sep-2024	Page	24 of 52
		IG1601	Statistical Analysis Plan								

7 Subject Disposition and Demographics

Unless otherwise noted, all demographics listings and summaries will be based on the ITT population. Subjects who were incorrectly stratified at the time of randomization will be listed and summarized.

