9.3.6 Number and Length of Hospital Readmission for an Acute Complication of Cirrhosis

All occurrences of hospital admissions are collected via eCRF through Month 12 and will be listed.

For each subject, the number of hospital readmissions due to acute complication of cirrhosis will be counted. This endpoint will be presented by treatment as a continuous variable and analyzed by Poisson regression with adjustment for overdispersion using the Pearson statistic to estimate the scale parameter. The total number of hospital admissions in the SMT + Albutein 20% treatment group will be compared to the SMT alone. The response variable in the model will be the total number of hospital admissions experienced by a subject while on treatment. The model will include treatment group, IWRS stratification factors of region (Europe or North America) and history of hospitalization for acute decompensation of liver cirrhosis (yes or no) as factors. The logarithm of the subjects' treatment duration will be used as an offset variable in the model to adjust for subjects having different exposure times during which the events could occur. The estimated treatment effect (ie, the incidence rate ratio of SMT + Albutein 20% versus SMT alone) and corresponding 95% confidence interval (CI) will be presented.

Hospital readmissions occurring on treatment are defined as any hospital admission that occurred with a start date/time on or after the subjects treatment start date/time (treatment start date/time is defined as; date/time of randomization (for SMT alone group) or commencement of Albutein (SMT+ Albutein treatment group) treatment). If time is missing and the incidence occurred on or after the date of randomization (for SMT alone group) or the date of commencement of Albutein (for SMT+ Albutein treatment group) treatment it will be considered to have occurred while on treatment. If the hospital readmission is on-going at the end of the study, it is also considered as occurring on treatment.

Number	BIG-CL-SP-000319		
	Version	2.0	Status
Effective Date	09-Sep-2024	Page	37 of 52
Effective			
GRIFOLS			
Bioscience Industrial Group			

In the event a hospital readmission occurs prior to treatment start date and the discharge date is after the treatment start date it will be counted as an occurrence.

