9.3.7 Number and Length of ICU Admission

For each subject, the number of hospital readmissions in which the subject was admitted to the ICU will be counted. This endpoint will be presented by treatment as a continuous variable and analyzed in the same way as hospital readmissions using Poisson regression with adjustment for over dispersion using the Pearson statistic to estimate the scale parameter.

ICU admission occurring on treatment are defined as any ICU admission that occurred with a start date/time on or after the subjects date/time of randomization (for SMT alone group) or commencement of Albutein (SMT+ Albutein treatment group) treatment. If time is missing and the incidence occurred on or after the date of randomization (for SMT alone group) or the date of commencement of Albutein (for SMT+ Albutein treatment group) treatment it will be considered to have occurred while on treatment.

In the event a ICU admission occurs prior to treatment start date, and the discharge date is after the treatment start date, it will be counted as an occurrence and the duration of this ICU admission will be calculated as [(discharge date – treatment start date) + 1].

For each subject, the total duration (days) of hospital readmission to the ICU will be calculated as the sum of the durations of each ICU admission (ICU discharge date – ICU admission date + 1). Descriptive statistics will be presented by treatment and analyzed by ANCOVA with adjustment for stratification factors. If a subject's ICU admission is considered on-going at the end of the study, the end of study completion date will be used to calculate the duration of the ICU readmission.

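### The paracentesis test relies on a Pearson-scaled Poisson standard error that is too small if need differs persistently between patients, because follow-up is unequal by design

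*SAP*

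**What the plan says.** SAP 9.2.6 counts each subject's on-treatment paracenteses. The rate is "analyzed using Poisson regression with adjustment for overdispersion using the Pearson statistic to estimate the scale parameter". On covariates, "The model will include treatment group, IWRS stratification factors of region (Europe or North America) and history of hospitalization" for acute decompensation. On follow-up, the logarithm of "treatment duration will be used as an offset variable in the model to adjust for subjects having different exposure times". The alternative hypothesis is that the rate on SMT + Albutein 20% "is less than the rate of occurrence of paracentesis procedures on SMT alone".

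SAP 6.5 states that "All statistical tests will be 2-sided with significance level fixed at 0.05". It places paracenteses sixth among the secondaries, where "each subsequent hypothesis is tested only if the superiority for the previous comparison(s) listed below has been demonstrated". The primary and five survival secondaries must therefore succeed first.

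The exploratory endpoints use the same method. Readmissions (9.3.6) are "analyzed by Poisson regression with adjustment for overdispersion using the Pearson statistic to estimate the scale parameter", and ICU admissions (9.3.7) use "Poisson regression with adjustment for over dispersion using the Pearson statistic to estimate the scale parameter".

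No robust variance or negative binomial model is named. The only sensitivity analysis for this endpoint is the per-protocol repeat (9.2.7.1), which uses the same standard error. Protocol 9.1.2.2 says only that count variables get a Poisson regression model.

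**The concern.** The Pearson scale is in effect the average over subjects of (count - mean)²/mean, with every subject weighted equally. Multiplying the Poisson variance by it is correct if Var = φ × mean with one φ for everyone.

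If some patients persistently need many procedures and others few, a natural description is Var = mean + k × mean². A subject's variance-to-mean ratio then grows with time at risk. Subjects with short follow-up have ratios near 1 and pull the average down, while the rate ratio is driven mainly by subjects with long follow-up. The resulting standard error is too small.

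Unequal follow-up is built into this trial: deaths, transplants (which end study treatment under protocol 5.3.2) and dropout all shorten exposure. At stake are the CI for the rate ratio and the error rate of a test that the SAP places under type I error control.

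**Working it through.** **Inputs from the documents (SAP 6.2, 6.5):** 205 per arm; one-year event rates 46% and 31%; dropout 20%; two-sided 5%.

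**Assumptions, because the documents are silent:** exponential event and dropout times; procedure rate r per year; gamma between-subject heterogeneity with variance k; at first, need unrelated to survival.

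**1. The plan's own figures.** For 46% against 31% with the chi-square test, 164 per arm gives power 0.79998, and 164/0.8 = 205 per arm. The hazard ratio is ln(0.69)/ln(0.54) = 0.6022. Both agree with SAP 6.2. The plan gives no rate, dispersion or power for paracenteses; the only figure for that test is the nominal 5%.

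**2. Exposure implied by the design.** Yearly hazards are -ln(0.54) = 0.616 (control), -ln(0.69) = 0.371 (Albutein) and -ln(0.8) = 0.223 (dropout). With total hazard h and follow-up T cut at one year:

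- E[T] = (1 - e^(-h))/h
- E[T²] = (2/h²)(1 - e^(-h)(1 + h))

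| | h | E[T] | E[T²] | CV² |
|---|---|---|---|---|
| Control | 0.839 | 0.677 | 0.583 | 0.27 |
| Albutein | 0.594 | 0.754 | 0.680 | 0.20 |
| Pooled 1:1 | | 0.715 | 0.631 | 0.234 |

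**3. Large-sample size of the error.** Under Var = mean + k × mean², true variance divided by planned variance is

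(1 + k r E[T²]/E[T]) / (1 + k r E[T]), which cannot exceed 1 + CV².

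With the pooled row, E[T²]/E[T] = 0.883.

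- r = 6, k = 1: (1 + 6 × 0.883)/(1 + 6 × 0.715) = 6.30/5.29 = 1.19. The planned SE is 1/√1.19 = 0.92 of the true SD. Type I error is 2(1 - Φ(1.96/√1.19)) = 7.2%.
- r = 6, k = 2: 11.59/9.58 = 1.21; SE ratio 0.91; type I error 7.5%.
- Upper limit: √1.234 = 1.111; type I error 7.8%.

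**4. Simulation of the SAP model** (205 per arm, both stratification factors, log T offset, true rate ratio 1, 20,000 trials per row):

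| r, k | Mean planned SE / true SD | Planned, two-sided | Planned, favouring Albutein | Sandwich, two-sided |
|---|---|---|---|---|
| 6, 1 | 0.108/0.120 = 0.90 | 7.6% | 3.8% | 5.3% |
| 6, 2 | 0.146/0.164 = 0.89 | 8.2% | 4.1% | 5.7% |
| 12, 2 | 0.142/0.160 = 0.89 | 8.0% | 4.0% | 5.4% |

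Two rows lie slightly above the large-sample limit. I read this as finite-sample behaviour of skewed counts, since the sandwich test is also a little above 5%. Negative binomial gave 5.9% (k = 1) and 5.1% (k = 2) at r = 6 in 1,500 trials each (Monte Carlo SE about 0.6 points), but gamma-Poisson data are its own model.

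**5. What the result depends on.**

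| Setting | Planned test, two-sided |
|---|---|
| Equal follow-up | 5.0-5.3% |
| Variance proportional to mean, same unequal follow-up | 5.2% |
| Mild overdispersion (Pearson scale 1.4-1.8) | 5.7-6.1% |
| Low rates, assumed 0.3-1 events/year | 5.6-6.5% |
| 40% dropout | 8.7-8.8% |
| Lognormal heterogeneity, k = 1 to 2 | 6.9-9.1% |
| High-need subjects leave sooner, equal hazards, weak to moderate link, k = 1 | 7.1-7.6% |
| Same, moderate link, k = 2 | 6.1% |
| Same, strong link | 4.1-4.6% |

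**6. Unequal survival (46%/31%) with need linked to death.** At r = 6 and k = 1-2, with moderate or strong links, the mean log rate ratio moves to +0.037 to +0.108, a ratio of about 1.04 to 1.11 when the truth is 1. This bias runs against Albutein, and false claims in its favour fall to 0.5-2.1%. Two-sided error is 8.0-9.5% with the planned SE and 7.1-11.8% with the sandwich, so a better SE does not cure it.

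**The case against.** **The SAP already adjusts for overdispersion.** It adds a Pearson scale, strata and an exposure offset to the protocol's plain Poisson model, and quasi-Poisson is an accepted method. This stands as far as it goes, but the adjustment assumes a variance form that persistent patient differences would violate.

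**Independence of need and survival is doubtful here.** Ascites is an index complication for transplant evaluation (protocol 5.3.2.1), transplant ends study treatment, and TIPS, considered for refractory ascites, may end it (protocol 4.4.1.2 and 5.3.2). If high-need patients leave early, the excess shrinks or reverses. This stands, and it makes the size conditional. It also means that the planned test's error rate moves with features nobody can verify beforehand: about 4% to 9% across these settings.

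**Only one direction gives a false claim.** This stands: the relevant excess is about 3.5-4.4% against 2.5%. The CI still undercovers where the SE is too small.

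**The gate limits the consequence.** Six survival tests must succeed first. Treating every event as a death, with exponential hazards and 20% dropout, 3-month log-rank power is about 41% and the chance of reaching test six about 35%. This stands as a limit on impact, but a paracentesis claim would be made precisely when the gate opens.

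**A reader might infer that varying follow-up alone inflates the error, or that the test runs at 7-9%.** The documents do not support either. They give no procedure rate or dispersion, unequal follow-up with proportional variance leaves the error at about 5%, and in these checks roughly 9% needed 40% dropout or lognormal tails. Nor do they support extending a breach of protected alpha to 9.3.6 and 9.3.7: both are exploratory and outside the sequence.

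**Conclusion.** The point holds conditionally. With persistent between-patient heterogeneity (gamma variance 1-2), 3-12 procedures a year and need unrelated to survival, the design's attrition makes the planned SE about 8-12% too small and two-sided type I error about 7-8.5%. If any of those assumptions weakens, the error moves towards 5%, and a strong link between need and early exit takes it below. Since none of them can be settled from the documents, the case for change is that a gated test should not rest on an unverified variance form when a near-free alternative avoids it. This is an inexpensive improvement to a secondary analysis; it does not touch the primary endpoint.

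**What to change.** In SAP 9.2.6, keep the Poisson mean model, the covariates and the log-duration offset. Base the CI and p-value on the subject-level empirical (sandwich) variance. Report the Pearson-scaled and negative binomial results as sensitivity analyses.

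The same change in 9.3.6 and 9.3.7 is optional, for consistency; the effect is small at low event rates.

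The cost is one SAP sentence, one line of code and a CI about 10% wider (0.120/0.108 = 1.11 at r = 6, k = 1). It needs no new data or subjects. It does not remove bias if survival differs between arms and high-need subjects die sooner, and the SAP should say so.

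While 9.2.6 is open, two related points need reconciling: its directional hypotheses against the two-sided rule in 6.5, and a treatment-duration offset that is not defined for the SMT arm against an on-treatment count with no stated end date.
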